### 2.2 Study design and participants

This is a single centre, 2-arm, 4 weeks randomised, double-blinded parallel trial with equal allocation ratios (1:1). We will follow the Consolidated Standards of Reporting Trials (CONSORT) recommendations for randomized trials (32). Participants will be PLWH (30-60 years) managed under the community-based model (Community Drug Distribution Points-CDDPs) in Wakiso district, central Uganda. The district encircles Kampala, Uganda's capital city with an estimated population of over 2.9 million people. The district has the highest prevalence (10%) of HIV in Uganda. Over 3,801 PLWH are currently receiving the HIV care from CDDPs in Wakiso District (33). The study inclusion and exclusion criteria are presented in Table 2. The study will be announced during the drug refill days and interested patients will be provided with more information about the study before obtaining their consent to participate.

Demographic and medical information will be collected from all consented patients,

[figure not shown]
The study participants will be randomly allocated to consume twice-daily 300 mL of either 10% or 30% pulp of T. indica fruit juice, **figure 1**. Both participants and the study team will be blinded to the intervention materials. Measurements will be performed at three different timelines: 1) Baseline, 2) Week two of the study, and 3) Endline (week four of the study).

Compliance to the study protocol will be confirmed by weekly telephone inquiries, and by counting the returned empty juice bottles or unused study products at each follow-up visit. Participants will be asked to maintain their habitual dietary regimen.

Any reported unusual gastrointestinal side effects, including abdominal pain/cramps, heartburn, stomach acid/reflux, nausea, vomiting, abdominal rumbling, bloating, belching, excess gas/wind, stool type, etc, during the study will be recorded. Patients will be encouraged to contact a study staff by phone or e-mail if they experience any adverse health-related impacts of the interventions. In the case of *T. indica* fruit juice intolerance, patients will be excluded.

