# 2.3.1 Study outcomes

The primary endpoint will be changes in Triglycerides (TG). Secondary outcomes will include changes in fasting blood glucose and plasma levels of lipids, and parameters of vascular function, **Table 3**.

Table 3: Study outcome measures

Primary outcome measures	Secondary outcome measures	Exploratory outcomes	
Triglycerides [mg/dL]	PWV [m/s], Blood pressure [mmHg]	BMI [kg/m²]	
	Facting Pland always [mg/dI]	Fat mass composition	
	Fasting Blood glucose [mg/dL]	Waist circumference [cm]	
	HDL-c, LDL-c, Total cholesterol [mg/dL]		
	AIx (%), MAP		

BMI, Body Mass Index; PWV, Pulse Wave Velocity; HDL-c, High Density Lipoproteins; LDL-c, Low Density Lipoproteins; AIx, Augmentation Index; MAP, Mean Arterial Pressure

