### 6. Statistical analysis

This is a proof-of-concept (no power calculation). The study will use a pragmatic sample size. Intention to treat analysis will be conducted. Continuous variables will be presented as mean and standard deviation. Student t-test will be applied to compare means of endpoints between patient groups. Outcome variables will be checked for normality and transformed where necessary. To account for any missing data, analyses will be conducted using linear mixed models. Analysis will be performed using the Statistical Package for the Social Science (SPSS) software version 22 (IBM Corp, Armonk, NY, USA). A p-value of <0.05 will be used for statistical significance.

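### Section 2.2 excludes participants who cannot tolerate the juice, apparently after randomisation, and section 6 does not reconcile this with the intention-to-treat analysis

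*Combined protocol and SAP*

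**What the plan says.** Section 2.2 randomises participants 1:1 to 300 mL twice daily of 10% or 30% pulp juice. "Measurements will be performed at three different timelines": baseline, week 2 and week 4. It then describes compliance checks, states that gastrointestinal side effects "during the study will be recorded", and ends with the rule on "fruit juice intolerance, patients will be excluded". It does not say what they are excluded from.

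Section 2.3.1 makes change in triglycerides the primary endpoint. Section 6 says "Intention to treat analysis will be conducted", without defining the analysis set. It names two methods: "Student t-test will be applied to compare means of endpoints between patient groups", and "To account for any missing data, analyses will be conducted using linear mixed models". Neither statement mentions participants excluded for intolerance.

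Table 2 (eligibility) has no intolerance criterion. Section 10 covers only participants who choose to leave.

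**The concern.** The only juice exposure in the visible text is the allocated product, and no run-in is described. The rule therefore reads as a removal after randomisation for a reason produced by the treatment being compared. If one arm loses more participants than the other, and those lost would have had a different triglyceride change, the arms that remain are no longer the arms that were randomised.

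Unequal loss is plausible because the juices differ in acidity, and section 2.2 lists heartburn and reflux among the effects to record. It is not shown: the documents give no tolerability data. Site staff cannot tell from the text whether to keep measuring an intolerant participant, and a measurement not taken at week 2 or week 4 cannot be recovered later.

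**Working it through.** The plan gives no sample size, intolerance rate or dropout figure, so there is no figure of its own to reproduce.

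**1. The possible meanings of excluded**

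| Meaning | Effect on the section 6 analysis |
|---|---|
| Removed from analysis | Contradicts intention to treat |
| Removed from follow-up | Week 2 and/or week 4 triglycerides are missing; the mixed model copes only if they are missing at random, and a completer t-test does not recover them |
| Juice stopped, measurements continue | No conflict |

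Nothing in sections 2.2, 6 or 10 or Table 2 chooses between them.

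**2. Could intolerance differ by arm?** Inputs are the titratable acidity in Table 1 and the daily volume in section 2.2 (2 × 300 = 600 mL).

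- 30% juice: 600 × 0.95/100 = 5.70 g/day
- 10% juice: 600 × 0.35/100 = 2.10 g/day, a ratio of 2.71

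This makes a difference plausible and no more.

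**3. Completers only, closed form.** All rates and correlations from here on are assumptions. Suppose a proportion p with the highest intolerance propensity is excluded, and that propensity has correlation r with the triglyceride change. With z the upper-p normal quantile and φ the normal density, the mean change among those retained is shifted by −r·φ(z)/(1−p) SD. The factor φ(z)/(1−p) is 0.109 at p = 5%, 0.195 at 10%, 0.350 at 20% and 0.497 at 30%. With no true effect and 5% excluded on the 10% juice, the bias (30% minus 10%, negative favouring the 30% juice) is:

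- 10% excluded, r = 0.3: −0.3 × (0.195 − 0.109) = −0.026
- 20% excluded, r = 0.3: −0.3 × (0.350 − 0.109) = −0.072
- 30% excluded, r = 0.5: −0.5 × (0.497 − 0.109) = −0.194
- Equal rates with equal r: 0

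**4. The planned mixed model, by simulation.** There were 20,000 null trials per setting (Monte Carlo error about 0.15 percentage points). Three visits had an assumed within-person correlation of 0.6. The model had arm-by-visit means and unstructured covariance, and used all recorded values. In every row 5% are excluded on the 10% juice, before week 2. Entries are bias in SD of change / type I error.

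| Excluded on 30% juice | r | 20 per arm | 40 per arm |
|---|---|---|---|
| 10% | 0.1 | −0.009 / 4.7% | −0.007 / 4.8% |
| 10% | 0.3 | −0.023 / 4.7% | −0.020 / 4.9% |
| 20% | 0.3 | −0.060 / 5.0% | −0.057 / 5.6% |
| 20% | 0.5 | −0.099 / 5.7% | −0.097 / 7.0% |
| 30% | 0.3 | −0.095 / 5.5% | −0.092 / 6.5% |
| 30% | 0.5 | −0.158 / 6.8% | −0.157 / 9.7% |
| 30% | −0.3 | +0.093 / 5.4% | +0.095 / 6.5% |
| 30% | 0 | −0.001 / 4.5% | +0.002 / 4.8% |

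Other settings:

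- Leaving after week 2 (20-30% excluded, r = 0.3 to 0.5): bias −0.049 to −0.138; type I error 5.1-6.5% at 20 per arm and 5.5-8.5% at 40. At r = −0.3 with 30% excluded, bias is about +0.08.
- Exclusion driven only by a recorded triglyceride value: −0.002 to +0.002; 4.5-5.1%.
- Completer t-test, 20-30% excluded, r = 0.3 to 0.5: −0.071 to −0.195; 5.7-8.6% at 20 per arm and 6.2-12.5% at 40.
- Everyone followed and analysed: −0.002 to +0.001; 5.0-5.2%.

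**The case against.** The strongest reply is that section 6 already deals with this: analysis is by intention to treat, missing values go to a mixed model, and nowhere does the plan say that anyone is deleted from the analysis. On that reading an intolerant participant simply stops. This is a possible reading, so the fault is an unreconciled rule and not a proven contradiction. But the plan does not adopt that reading. If follow-up ends, the mixed model protects only under missing at random.

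Second, Figure 1 is not available and the text just before the allocation sentence breaks off, so a run-in or tasting step cannot be ruled out. That stands as a limit on certainty. Even so, intolerance arising during the study would still need a rule for the data.

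Third, the bias may be negligible. At 20 per arm the standard error of a difference in change is about √(2/20) = 0.32 SD. The worst case tabulated, 0.158, is half of that, and the mild case of 0.023 is under a tenth. The worst case also needs 30% versus 5% exclusion and a correlation of 0.5, which nothing in the documents supports. This is fair, and it limits the severity. The main simulation also describes lost follow-up; outright deletion from the analysis is closer to the completer figures.

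Fourth, measuring people off juice dilutes the dose contrast that the second hypothesis addresses. That is a real cost of the fix.

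**Conclusion.** The point holds and should be fixed, although it does not undermine the trial. As written, section 2.2 allows randomised participants to be dropped or no longer measured for a reason tied to their allocated juice, and section 6 does not say otherwise.

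The size is uncertain. Bias is about zero if intolerance is unrelated to triglyceride change or depends only on recorded triglycerides. It is trivial at 5% versus 10% exclusion. In the planned mixed model it is 0.05 to 0.16 SD of change at 5% versus 20-30% with correlation 0.3 to 0.5, with type I error of 5.0-6.8% at 20 per arm and 5.5-9.7% at 40. The direction reverses if the correlation is negative. Every rate, correlation and sample size here is assumed.

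Confidence is medium, because Figure 1 is not available and one reading of the rule is harmless.

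**What to change.** Reconcile sections 2.2 and 6.

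- **Section 2.2:** define excluded, and add: *Intolerance does not remove a participant from follow-up or analysis. Those who consent are still measured at the scheduled week 2 and week 4 visits.* When the juice is stopped remains for the investigators.
- **Section 6:** add: *All randomised participants are analysed in their assigned arm, using the planned linear mixed model with all recorded triglyceride values. Any analysis restricted to tolerators is a sensitivity analysis. Intolerance and missing outcomes are reported by arm within the CONSORT reporting.* Modelling baseline as a response is one option, not a requirement.

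The minimum edit is the definition of excluded and a statement that intention to treat means everyone randomised. Naming the mixed model for triglycerides goes slightly further, since section 6 also names a t-test, but the mixed model is already planned for missing data.

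The cost is a few sentences and at most two already scheduled visits per affected participant: 2 × USD 8 = USD 16 for transport (section 7), plus the snack and testing at each. The price in interpretation is that the estimate then includes time off juice.

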# Randomisation and blinding

A biostatistician of Mildmay hospital will develop computer-generated sequence to randomly allocate participants to each of the two study arms, as shown in figure 1. The biostatistician responsible for generating the allocation sequences will not have any study-related tasks, for example, inclusion or examination of participants. The two juice prototypes will be blinded by assigning a secret code to each of the intervention products. As such, blinding of the investigators and participants will be undertaken to ensure a double-blind intervention. Moreover, the statistical analyses of the main endpoints will be done before breaking the intervention product concealment.

BP, Blood Pressure; BC, Body composition; FBG, Fasting Blood Glucose; TG, Triglycerides; Tc, Total cholesterol; PA, Physical Activity; PWV, Pulse Wave Velocity; WC, waist circumference.

Figure 1: Schematic overview of the study protocol.

Table 2: Eligibility criteria for study participants

Inclusion criteria	Exclusion criteria			
Triglycerides ≥150 mg/dL	Taking dietary supplements			
TLD regimen (ART) for ≥12 months	TB co-infection, renal failure disease, liver cirrhosis, chronic pancreatitis			
95% ART adherence in last 6 months 	Pregnancy and Lactation or regular sport activity			
Virally suppressed (most recent results viral load suppressed within the last 12 months) 	Parallel participation in another clinical trial			
PLWH aged ≥30≤60 years.	On treatment for; dyslipidaemia, hypertension or			
No plans to change location in the next 6 months	diabetes and oral hypoglycaemic drugs			
	Very low blood pressure (< 90/50 mmHg)			
	Not willing to consent or unable to consent			

ART, Antiretroviral Therapy; DBP, Diastolic blood pressure; FGD, Focus group discussion; SBP, systolic blood pressure; TLD, Tenofovir Lamivudine Dolutegravir; WC, waist circumference.

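### The plan states no protection against chance imbalance in entry triglycerides: the type of allocation sequence is unspecified and no analysis names a baseline term

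*Combined protocol and SAP*

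**What the plan says.** Section 2.2 describes a "2-arm, 4 weeks randomised, double-blinded parallel trial with equal allocation ratios (1:1") at one centre. The section on randomisation and blinding gives the method as a "computer-generated sequence to randomly allocate participants to each of the two study arms" and refers to Figure 1, which is not reproduced in the text available for review. It adds that "The biostatistician responsible for generating the allocation sequences will not have any study-related tasks", and that blinding works by "assigning a secret code to each of the intervention products", which means two codes for the whole trial. The readable text mentions no blocks, strata or minimisation. It also does not call the sequence simple.

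Table 2 requires triglycerides of at least 150 mg/dL and sets no upper limit. Section 2.3.1 makes change in triglycerides the primary endpoint. Section 6 gives no power calculation and states: "The study will use a pragmatic sample size". It plans a Student t-test between groups and linear mixed models to handle missing data, and names no baseline covariate for either.

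**The concern.** Chance imbalance can be limited at allocation, by blocking and stratifying, or in the analysis, by adjusting for baseline. The written plan commits to neither for the variable that matters most. Every participant has a qualifying triglyceride value before allocation, and with a floor but no ceiling those values may spread widely.

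A change score does not neutralise a baseline gap. If the arms start d SD apart and the baseline-endline correlation is ρ (equal variances), the expected difference in change moves by (1 − ρ)d in the opposite direction. A gap of 0.5 SD therefore shifts the estimate by 0.25 SD at ρ = 0.5 and by 0.15 SD at ρ = 0.7. In a small proof-of-concept trial judged by "A p-value of <0.05 will be used for statistical significance", a shift of that size could colour the reading of the only primary result.

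**Working it through.** The plan has no figure of its own to reproduce: it states no total, effect size or SD.

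**Inputs.** From the documents: two arms, 1:1, change in triglycerides as primary endpoint, t-test between groups. Assumed: totals N of 20 to 100, baseline triglycerides normal on the analysis scale, ρ of 0.5 to 0.7, and simple randomisation as the unprotected case.

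**Step 1, arm sizes.** With a participants in one arm, a ~ Binomial(N, ½). Information relative to an equal split is 4a(N − a)/N², with expectation 1 − 1/N.
- N = 20: average loss 1/20 = 5%. A split of 14:6 or worse has probability 11.5%; at 14:6 the loss is 1 − 4×14×6/400 = 16%.
- N = 40: average loss 1/40 = 2.5%. A split of 24:16 or worse has probability 26.8%; at 24:16 the loss is 1 − 4×24×16/1600 = 4%.
- N = 100: average loss 1%. A split of 60:40 or worse has probability 5.7%.

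Uneven arms are therefore common in a small trial but cheap on average.

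**Step 2, baseline triglyceride gap.** With near-equal arms the difference in baseline means has SD 2/√N in SD units, so P(gap ≥ 0.5 SD) = 2[1 − Φ(0.5√N/2)]. At N = 20 this is 2[1 − Φ(1.118)] = 26%; at N = 40, 2[1 − Φ(1.581)] = 11%; at N = 60, 2[1 − Φ(1.936)] = 5%. Simulation (6,000 trials per setting; 50% or 70% of one sex) lets arm sizes vary:

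| Total N | Simple | Blocks of 4, no strata | Blocks of 4 in four strata |
|---|---|---|---|
| 20 | 27% | 26–27% | 11% |
| 40 | 12% | 12% | 1.4% |
| 60 | 5–6% | 5.5% | 0.2% |

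The four strata are sex by triglycerides above or below the median. Blocking alone equalises arm sizes but does nothing for the triglyceride gap; stratifying does. At N = 20, incomplete blocks in four strata still leave a 60:40 or worse split in 8–10% of trials, against 50% with simple randomisation.

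**Step 3, value of adjustment.** For unit variances, the variance of a change score is 2(1 − ρ), and after continuous baseline adjustment it is 1 − ρ². The ratio is (1 + ρ)/2: 0.75 at ρ = 0.5 and 0.85 at ρ = 0.7, a large-sample reduction of 25% and 15%. Simulation at N = 20 to 60, compared with simple randomisation and an unadjusted t-test on change, gives reductions of about 7–26% for continuous adjustment alone and about 9–22% for stratified blocks with the stratum terms in the model. Small totals lower the gain because the slope must be estimated, and simulation error widens the range.

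**The case against.** A reader might infer that randomisation is unrestricted. The documents do not say so: a computer-generated list can be blocked or stratified, and Figure 1 cannot be checked. What is established is that the type is not stated.

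A reader might also infer that the stated 1:1 ratio will not be delivered. But 1:1 is an allocation ratio, which simple randomisation with probability ½ honours; it merely does not guarantee equal counts. Nor is a small total established. It is an inference from the proof-of-concept label and the pragmatic size, and by N = 100 marked imbalance is uncommon.

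The strongest objection is that chance imbalance does not bias a randomised comparison, and that continuous baseline adjustment captures most of the benefit with no change to the list. Both parts are correct. A mixed model can also be set up to account for baseline. But section 6 does not say that it will be; it gives the mixed model only the role of handling missing data. The objection therefore shows which half of the remedy matters most, and does not show that the plan already contains it.

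The case for stratifying by sex is weaker. The documents give neither the expected sex mix nor any link between sex and the outcomes, and more strata mean more incomplete blocks.

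**Conclusion.** The concern holds in limited form. The written plan states no protection, at allocation or in the analysis, against chance imbalance in a variable that is both known at entry and primary. If the list is simple, a gap of at least 0.5 SD arises in about 27% of trials at N = 20 and 12% at N = 40; average precision lost to uneven arms is only about 5% and 2.5%. The comparison remains unbiased. These sizes depend on the assumed totals, the assumed simple list and normality on the analysis scale. The variance gain also depends on ρ of 0.5 to 0.7. It would go too far to say that stratified blocks solve the problem outright: at N = 20 an 11% chance of a 0.5 SD gap remains in the four-stratum simulation. The change is worth making before enrolment, since allocation cannot be redone afterwards.

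**What to change.** **Randomisation and blinding.** State that the sequence uses random permuted blocks of varying size, not disclosed to enrolling staff, stratified by entry triglycerides above or below a cut fixed in advance. Add sex as a second stratum only if the planned total is not very small. Label bottles by participant number and not by one code per product: with two visible codes, staff can follow the run of allocations and could guess the end of a short block.

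**Section 6.** State the planned total. Make the linear mixed model the primary analysis in place of the unadjusted t-test, with baseline triglycerides as a continuous covariate plus any stratification factor. The dichotomised stratum should not stand in for the continuous value.

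**Cost.** A few lines in the list program, one or two model terms, somewhat more list and label management, and some incomplete blocks. If the list is already blocked or stratified, the first change is only a matter of writing the rule down; the model change is needed either way.

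### Table 2 excludes people treated for dyslipidaemia, hypertension or diabetes but sets no upper limit on untreated triglycerides, fasting glucose or blood pressure

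*Combined protocol and SAP*

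**What the plan says.** Section 2.2 names Table 2 as the place for the eligibility criteria. On the three markers, Table 2 says this:

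- Triglycerides: an inclusion floor, "Triglycerides ≥150 mg/dL", with no maximum.
- Blood pressure: one exclusion, at the low end, "Very low blood pressure (< 90/50 mmHg".
- Fasting glucose: no criterion.
- Treatment status: an exclusion that begins "On treatment for; dyslipidaemia, hypertension or" and continues with diabetes and oral glucose-lowering drugs. It depends on being treated, not on a measured value.
- Diagnoses: "TB co-infection, renal failure disease, liver cirrhosis, chronic pancreatitis".

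For the period after entry, section 2.2 states "Measurements will be performed at three different timelines": baseline, week 2 and week 4. It also states "Compliance to the study protocol will be confirmed by weekly telephone inquiries" and "Patients will be encouraged to contact a study staff by phone or e-mail if they experience any adverse health-related impacts of the interventions". It provides for recording gastrointestinal effects and for excluding patients who do not tolerate the juice. Sections 2.4.1 and 2.4.2.2 describe how the markers are measured. Section 10 covers voluntary withdrawal only.

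**The concern.** The criteria require raised triglycerides and remove everyone already on treatment for the three conditions. The people who remain are untreated, and no rule keeps a severe value out. The protocol does set a blood pressure limit, but it guards against low pressure only. High pressure, very high triglycerides and high glucose are left open.

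What is at stake is participant safety. Untreated people would have all three markers measured by the trial team, and the readable plan attaches no action to a high result, either at entry or later. Section 1.1 gives reason to expect raised values in this kind of population: an earlier sample under the community care model had raised fasting glucose in 49.6%, high blood pressure in 31.5% and hypertriglyceridaemia in 26.4%.

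**Working it through.** The plan gives no figure to reproduce here. Section 6 states that there is no power calculation, and the protocol gives no sample size or SD. The check is a reading of every row of Table 2, then of the other sections for a limit placed elsewhere.

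**Step 1. Limits in Table 2.**

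| Marker | Lower limit | Upper limit |
|---|---|---|
| Triglycerides | 150 mg/dL (inclusion) | none |
| Blood pressure | 90/50 mmHg (exclusion below) | none |
| Fasting glucose | none | none |
| Count | 2 of 3 | 0 of 3 |

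**Step 2. Do other Table 2 rows act as ceilings?** No. Chronic pancreatitis, renal failure and cirrhosis are diagnoses, and a person can have a severe marker value without any of them. Viral suppression and ART adherence concern HIV control.

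**Step 3. Is there a limit or referral rule elsewhere?** None is readable. In section 2.2 the calls check compliance, adverse effects are self-reported, and exclusion is for intolerance. Sections 2.4.1 and 2.4.2.2 are measurement procedures. Section 10 lets the participant leave but gives the team no trigger to act.

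**Step 4. What cannot be read.** Figure 1 is not shown. The section 2.2 sentence that starts "Demographic and medical information will be collected from all consented patients" is interrupted by a figure. The consent pages were removed. Any of these might hold a referral step. The abbreviation key under Table 2 defines SBP and DBP, which no readable row uses. It also defines WC and FGD, equally unused, so it may be a leftover, but a lost row cannot be ruled out.

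**Step 5. How many people?** This cannot be derived. The percentages in section 1.1 count raised values, with neither severity nor treatment status, and no sample size is given to multiply them by.

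**Step 6. Effect of a fix on the primary endpoint (change in triglycerides, section 2.3.1).** There are two routes.

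- A triglyceride ceiling cuts the upper tail of the baseline distribution. That may alter the mean change, its variance and the amount of regression to the mean. It acts before randomisation, so it applies to both arms alike.
- A referral after randomisation may lead to a new drug before endline. If the exclusion covers baseline values as well as screening values, the first referral of a randomised participant is at week 2. A drug started on that referral then runs for at most 4 − 2 = 2 weeks before the last triglyceride value, and for 4 − 4 = 0 weeks after a week-4 referral. If only screening values were covered and baseline were a separate visit, the first figure could approach 4 weeks. These figures assume that baseline precedes randomisation and that the markers are measured at week 2.

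**The case against.** The strongest reply is that a ceiling alone treats nobody. Nothing in the readable protocol withholds or delays care, participants may leave at any time, and the exposure is four weeks of a food product. A person with a severe untreated value is worse off for joining only if the trial finds the value and does nothing, which is the referral question, and the documents do not settle it. This stands in part: most of the safety gain comes from exclusion together with referral, and the fix should pair them. It does not remove the point, because a referral step found elsewhere would still not be an eligibility limit.

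A second reply is that Table 2 may not be fully readable, given the unused SBP and DBP entries in its key. That is a fair caveat on the blood pressure count. It does not bear on triglycerides or glucose.

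A third is that the risk is unquantified and mitigated: participants are in ongoing HIV care, virally suppressed, and free of several serious diagnoses. These features reduce the risk but limit none of the three markers.

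Stronger readings are tempting, and the documents do not support them:

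- A reader might infer that the trial has no referral rule. The missing figure, interrupted sentence and consent pages prevent that conclusion.
- A reader might take 49.6%, 31.5% and 26.4% as the share at risk. They describe raised values, not severe untreated ones.
- A reader might infer that the juice endangers people with high glucose. Table 1 lists Brix 6.80 for both juices. At 600 mL a day this is about 6.8 × 6 = 40.8 g of soluble solids (taking density as about 1), the same in both arms. Brix does not separate sugar from other solids, and the documents give no evidence of harm.

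**Conclusion.** The concern holds in a bounded form. In the readable eligibility criteria, 0 of 3 markers have an upper limit, while treated patients are excluded, so a severe untreated value does not bar randomisation. This is a safety gap in a stated rule, and the sponsor should close it.

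The size in people cannot be stated. The conclusion rests on Table 2 being complete as read, with the SBP and DBP caveat above. It does not depend on whether a referral rule exists elsewhere. A reader might also infer that the missing ceilings bias the comparison between arms. Nothing supports that, since the criteria apply equally to both arms before allocation. Nor is a claim about precision possible without a sample size or SD.

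**What to change.** **Table 2.** Add an exclusion for triglycerides, fasting glucose or blood pressure above numeric levels at screening or at a pre-randomisation baseline visit. People above a level are referred to care and not randomised. The sponsor's clinicians fix the levels before enrolment. As assumed, illustrative ranges for them to confirm (the documents give none): triglycerides 500–1000 mg/dL, blood pressure 160/100 to 180/110 mmHg, fasting glucose 126–250 mg/dL.

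**Section 2.2.** State that the same levels trigger referral at week 2 and week 4, without unblinding. The participant stays in follow-up and in the intention-to-treat analysis, with all observed values used. Any drug started, and its date, is recorded. If Figure 1, the interrupted sentence or the consent form already contains a referral step, state it here and still add the ceilings.

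**Optional.** One sensitivity analysis of triglycerides that sets aside values after a lipid-lowering drug is started, using the linear mixed model already planned in section 6.

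**Cost.** A short amendment. Table 2's own limits already require triglycerides and blood pressure, so neither needs a new test. Glucose comes from the section 2.4.1 device, assuming it is used at screening. The downsides are a slightly smaller eligible pool, a truncated upper tail of baseline triglycerides with the possible effects on the endpoint described above, and results that do not extend above the ceilings. A few participants may start treatment during the trial; without a sample size their weight in the analysis cannot be stated.
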